## 2.3. Synopsis

HBCOVID03 is a phase 2 randomized, placebo-controlled, double-blind clinical trial to assess efficacy of allogeneic adipose-derived mesenchymal stem cells (HB-HB-adMSCs) to treat symptoms of Corona Virus-19 (COVID-19) in patients suspected to have COVID-19. Developing effective interventions for COVID-19 requires incremental improvement of theoretically sound treatments based on systematically accruing data. Often such incremental development is hampered by statistical tools not appropriate to the task. Classical,

Frequentist statistics have advanced the field, but are less informative for the initial evaluation of a new treatment. The reliance of the Frequentist framework on dichotomous, null hypothesis-testing provides some control of the error rate in the context of multiple repeated trials; however, this is not what early-phase treatment testing requires. Developing nascent treatments requires investigators to bet on an alternative hypothesis. Investigators evaluating a theoretically sound intervention want to know the probability that the approach confers some level of benefit given the observed data: that is, they want to know the probability that the alternative hypothesis is true. While Frequentist inference does not directly address this issue, Bayesian statistical inference provides a principled approach to answer this question. Indeed, addressing the so-called “Pipeline Problem” in developing clinical applications, the FDA has indicated that Bayesian statistics offers one avenue for improved methodological efficiency.

Decision-making, based on an initial treatment trial, is assisted by estimates of the probability of an effect of some specified magnitude. These statements, not part of the conventional, Frequentist statistical lexicon, are accessible via Bayesian approaches, particularly with small sample sizes. Detailed descriptions of Bayesian statistical reasoning exist elsewhere. Succinctly, Frequentist models estimate the probability of observing the data (or data more extreme) given that the null hypothesis is true; Bayesian analyses estimate the probability of the alternative hypothesis given the observed data. Bayesian probability estimates incorporate prior information about plausible parameter values (i.e., the prior distribution) and the observed data (i.e., the likelihood). Combining these two distributions forms the posterior distribution which permits evaluation of the probability that the true value of the parameter falls in some range.

## **2.4. Statistical Hypotheses**

The null hypothesis is treatment with HB-adMSCs does not cause changes in primary and secondary endpoints (see outcomes) for suspected Corona Virus Disease. The alternative hypothesis for this study is that HB-adMSC treatment does result in changes from baseline values of primary and secondary endpoints in patients with suspected Corona Virus Disease. Hypotheses will primarily use Bayesian inference. (Any frequentist analyses performed as supplement will consider the hypothesis two-sided and tested at the 5% significance level.)

## **3. PLANNED ANALYSES**

### **3.1. Final Analyses**

The final planned primary analyses will be performed after the completion of the following sequential steps:

1. All participants have completed (or withdrawn from) the study as defined in the protocol.
2. All required database cleaning activities have been completed and final database release and database lock has been declared by Data Management.

## 4. ANALYSIS POPULATIONS

Population	Definition / Criteria	Analyses Evaluated
Safety analysis set	

• All randomised subjects who received at least one dose of HB-adMSCs infusion or placebo.

• If participants receive a treatment different to their randomized treatment, they will be analysed according to the treatment actually received.

	

• Safety

• Study Population

Efficacy analysis set	

• All randomized participants who received all 4 infusions of HB-adMSCs or placebo.

• Participants will be analysed according to their randomized treatment.

	

• Efficacy

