Patients will be considered to have completed the study if they complete treatment and assessments through day 28. A patient's investigational treatment should be discontinued if any of the following situations occurs:

- The Investigator believes that for safety reasons, it is in the best interest of the patient to stop treatment.
- The patient is non-compliant with the study visit schedule or other protocol requirements.
- The patient develops a severe allergic reaction that occurs following investigational product administration.

A patient may voluntarily withdraw or be withdrawn from the study at any time for reasons including, but not limited to, the following:

- Patient withdrawal of consent: At any time, a patient's participation in the study may terminate at his/her request. The specific reason for patient withdrawal will be noted on the case report form (CRF).
- Lost to follow-up: The patient stops coming for visits, and study personnel is unable to contact the patient after repeated attempts (e.g., mail, or email).
- This study may be terminated at the discretion of the Sponsor or any regulatory agency.

If a patient's infusions are discontinued at any point during the trial and the patient maintains consent to contribute additional outcome information, the patient should continue to be followed through day 28 for all safety and efficacy assessments. Investigators will be trained about the importance of retention and steps to prevent missing data. The date and reason for withdrawal are to be documented in the CRF. The study site(s) must immediately notify the medical monitor. The patients who withdraw prematurely must attend an early discontinuation visit if possible, at which time they will complete all assessments described in Table 2 under day 28. Unless the patient declines (consent withdrawn), the follow up phone call at day 28 should be done in all patients who were enrolled in the study regardless of their enrollment status.

In the event that a patient discontinues prematurely from the study due to an Adverse Event (AE) or serious AE, the event will be followed until it resolves (returns to normal or baseline values) or stabilizes, or until it is judged by the Investigator to be no longer clinically significant. Once a patient is withdrawn from the study, the patient may not re-enter the study.

Treatments

Details of the investigational product

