participant. This role will be referred to as ‘mixer’. Participants’ names are not disclosed to the mixer and the unblinded information will only be known to the randomizer. Is with knowledge of bag contents will be the designated mixer.

Blinding for Clinical Evaluators

To minimize assessment bias, clinical evaluators (data analysts and physicians) will be trained on how to maintain blinding to treatment as best as possible. “Best as possible” means that blinding will be maintained unless an adverse event occurs that requires unblinding the physician, which is determined by the medical monitor or DSMB. Training includes review of the process of blinding, describing who will be responsible for assigning product for the appropriate group, labels that will be used to identify subjects but not treatment group, and the process that should be followed if an adverse event occurs, triggering review by medical monitor and/or DSMB.

Planned Unblinding

Unblinding of patient information will only occur in the case of adverse event suspected to be related to the investigational product, per the medical monitor and DSMB.

Regulatory authorities and/or the IRB may request the unblinding of data from one or more patients at any time.

Investigational Product Assignment and Infusion Schedule (Staggering)

Each patient will be allocated a unique subject number at screening and will retain this number throughout the study.

The Investigational Product is to be administered to all eligible, enrolled patients in Arm 1.1 and Arm 2.1 by intravenous infusion at a dose of 1×10^8 cells at days 0, 3, 7, and 10. Every effort should be made to adhere to the dosing schedule. However, a scheduled infusion should not be administered if a patient has an ongoing AE that, in the Investigator’s opinion, warrants holding the infusion.

Prior and concomitant conditions

The investigators should document all prior significant medical history. Additional conditions present at the time when informed consent is given and up to the time of first infusion (Day 0) are to be regarded as concomitant conditions. Illnesses first occurring or detected during the study and/or worsening of a concomitant condition during the study should be documented as AEs in the CRF. The exception is that results from COVID-19 testing will be added to the CRF as part of medical history.

Prior and concomitant medications

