- Elevation or decrease in pulse of 20 bpm or more from baseline
- Change from baseline respiration rate in non-ventilated subjects

Study Alteration Rules

If any of the following events listed below occur, administration of the study drug will be immediately suspended. The Internal Monitoring Committee (IMC), presided by the Medical Monitor will meet to review the incident and its etiology. The committee determine if it is likely related to the drug, the infusion or unrelated. If the IMC along with the Medical Monitor agree that the SAE is unlikely or unrelated to the drug, the study will be continued. If the SAE appears to be definitely drug-related, the study will be stopped. If the SAE is probably or possibly linked to the drug, the IMC will determine the risk to future patients and decide if the study should proceed or be stopped.

Study Stopping Rules

The stopping rules listed below will trigger cessation of enrollment and potential study closure pending a comprehensive DSMB safety review.

1. Any infusion related death, deemed by PI to be associated or possibly associated with study drug.
2. Three or more of the same Grade 3 or higher AEs (judged by the investigator, medical monitor or sponsor), including infusion site reactions.
3. Any event which, in the opinion of the investigator, medical monitor or sponsor, contraindicates further dosing of additional subjects.
4. An infusion related, sustained (over 1 minute) episode of hypoxia (SaO₂ of less than 80%).
5. Any Grade 4-5 Adverse Event as defined in the NCI CTCAE v4.0 and determined to be temporally related to the HB-adMSC infusion by the Medical Safety Monitor and/or DSMB.

After such review, resumption of dosing may be considered, including consideration for any prophylactic interventions (e.g. antihistamines or corticosteroids for injection site reactions).

Medical Monitoring

Medical Monitor

It is the responsibility of the Principal Investigator to oversee the safety of the study at his/her site. This safety monitoring will include careful assessment and appropriate reporting of adverse events as noted above. At Hope Biosciences Stem Cell Research Foundation, [name], MD [contact] will be responsible for reviewing any reported AEs and SAEs to determine if changes to the study need to be made or if the study should be stopped for the protection of patients.

Data Safety Monitoring Board

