Safety is assessed by primary and secondary endpoints. Primary safety endpoints include incidence of adverse and serious adverse events. Secondary safety endpoints include incidence of specific adverse events including serious infections, infusion-related reactions, hepatotoxicity, heart failure, and cytopenias. Clinically significant changes in laboratory values, vital signs, weight, and physical examination results will also be measured.

Clinical efficacy is assessed by primary and secondary endpoints. Primary endpoints include the change from baseline in inflammatory markers (IL-6, D-dimer, C Reactive protein), time to clearing PCR test, change from baseline oxygenation, and time to return to room air (RTRA). Secondary endpoints include change from baseline of chest x-ray, change from baseline of CT scan, change from baseline of clinical laboratory values, adverse and serious adverse events, change in exploratory markers, and change in ordinal scale.

Analysis Population

Safety: All subjects receiving at least one infusion will be included for safety analysis.

Efficacy: All subjects receiving all four infusions will be included for efficacy analysis.

Additional sub-analysis will be performed comparing subjects receiving any other experimental treatment for COVID-19, to those who are not, in the following items:

- Change from baseline oxygenation
- Change from baseline chest x-ray
- Change from baseline CT scan
- Time to clearing PCR test
- Change from baseline inflammatory markers (IL-6, D-dimer, C Reactive protein)
- Change from baseline in IL-10
- Change from baseline in CD4:CD8 ratio
- Change from baseline in CD3⁺CD56⁺
- Change from baseline in VEGF
- Change from baseline in the 7-point ordinal scale

Demographic and Baseline Characteristics

Information describing subjects' gender, race/ethnicity, and age will be displayed in tables similar to the ones included below. The number and percent of the total sample population will be calculated for each demographic category.

Demographics	Female		Male		Both Genders	
Race/Ethnicity	N	%	N	%	Total	%
White						
Black or African American						
Hispanic or Latino						
Other (Specify)						
Total						

The mean, minimum, and maximum age at enrollment will be determined using standard calculations. The number and percent of total subjects in each age group will be calculated and reported.

Age at Enrollment	N	%
Mean		
Minimum		
Maximum		
	N	%
≥ 18 years		
18-21 years		
22-29 years		
30-39 years		

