#### 7.1.3. Population of Interest

The primary efficacy analyses will be based on the efficacy analysis set population, unless otherwise specified.

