#### **7.1.4.1. Statistical Methodology Specification**

Initial analyses examining group differences for baseline variables will use cross-tabulation, ANOVAs, and examination of correlations between baseline variables and specified outcomes. For the purposes of evaluating the comparability of groups, a posterior probability of  $\geq 75\%$  will constitute evidence for statistically reliable differences. Baseline or demographic variables on which group differences are detected, and which are correlated with outcomes, meet the definition of confounders and will result in two sets of analyses: one in which only the stratification variables are included as covariates, and another where the relevant variable is included as a covariate. This will permit determination of the degree to which any group differences might confound conclusions regarding treatment. A third set of analyses will model the effect of treatment group (controlling for stratification variables) on each outcome, focusing on the subgroup of patients who survived through the last infusion visit where statistically feasible.

Broadly, the data analytic strategy will use generalized linear, multilevel, and survival/cox proportional hazard models (R v 4.1, 2021; brms v 2.17; RStan v 2.21) for discrete, continuous, and time-to-event outcomes. Multilevel generalized linear modeling to account for clustering of patients within site and repeated observations within patients will evaluate continuous, dichotomous, and count data. All analyses will address potential missingness through joint modeling of observed outcomes and the missing data, an approach robust to ignorable missingness (i.e., MCAR and MAR). Sensitivity analyses will evaluate robustness of analytic conclusions to missing data. Non-ignorable missing data patterns will be addressed through pattern-mixture modeling methods.

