### 7.2.3. Population of Interest

The secondary efficacy analyses will be based on the Efficacy analysis set population, unless otherwise specified.

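### The efficacy set keeps only patients given all four infusions, so deaths and stopped or withheld treatment before the fourth leave every primary and secondary efficacy comparison after randomisation

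*SAP*

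**What the plan says.** SAP section 4 defines the efficacy analysis set as "All randomized participants who received all 4 infusions of HB-adMSCs or placebo", analysed by randomised arm. The protocol, under Analysis Population, agrees: "Efficacy: All subjects receiving all four infusions will be included for efficacy analysis".

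The set is then applied throughout. SAP 7.1.3: "The primary efficacy analyses will be based on the efficacy analysis set population, unless otherwise specified". SAP 7.2.3: "The secondary efficacy analyses will be based on the Efficacy analysis set population, unless otherwise specified". SAP 5.7 uses it for efficacy generally. The escape clause in 7.1.3 and 7.2.3 is never used to name a wider set. The only other efficacy population, in SAP 7.1.4.1 and 7.2.4.1, is survivors to the last infusion, which is no wider.

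Infusions are due on Days 0, 3, 7 and 10. Under the infusion schedule, "a scheduled infusion should not be administered if a patient has an ongoing AE" where the investigator judges that it warrants holding the dose. The withdrawal section lists reasons for discontinuing treatment. It adds that, if infusions stop but consent continues, "the patient should continue to be followed through day 28 for all safety and efficacy assessments". On missing data, SAP 7.1.4.1 states: "All analyses will address potential missingness through joint modeling of observed outcomes and the missing data".

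**The concern.** The primary model uses Visits 2 to 5, that is Day 0 to Day 10. Membership of the set therefore depends on what happens to the patient during the whole primary evaluation period. Death, an ongoing adverse event, discontinuation for safety and withdrawal can all relate to outcome, and their frequency can differ by arm.

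If more sick patients lose infusions on cells than on saline, the cell arm looks better than it is. The opposite split makes it look worse. If early discharge also ends infusions, early recoverers drop out too and part of a real benefit could be hidden. The documents do not settle that last point: the schedule replaces only the Day 28 visit with a telephone call.

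Membership is also unclear at the margin. The Infusion Stopping Rules halt an infusion already under way, and one trigger, "Change from baseline respiration rate in non-ventilated subjects", lies close to the oxygenation and room-air endpoints. Neither document says whether a part-given infusion counts as received.

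**Working it through.** **Passages side by side**

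1. Patients who stop infusions but keep consent are followed for efficacy to Day 28, yet the efficacy set leaves them out.
2. Joint and pattern-mixture models can act only on patients in the set. They cannot restore those whom the definition removes.
3. The separate survivor analysis implies that the main analysis includes deaths. Under SAP section 4, nobody who died before the fourth infusion is in it, so the survivor analysis is nearly redundant.
4. Death is category 1 of the ordinal scale, but within this set it can occur only after the fourth infusion.

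**Inputs from the documents**

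- 100 patients, 60 active and 40 placebo (protocol, Investigational Plan; 3:2 in SAP 2.2).
- 15% drop-out (protocol synopsis), not split by arm and not defined as missed infusions.
- The sample size of 100 cannot be re-derived. It rests on anticipated demand, with no effect size, SD, event rate or power. If drop-out equals missed infusions, the set has 100 × 0.85 = 85 patients (60 × 0.85 = 51 and 40 × 0.85 = 34).

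Everything below is assumed, for illustration. The SAP sets no efficacy success threshold, so 'positive' here means a posterior probability of benefit above 95%.

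**Room-air proportion, no true effect**

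Let p be the proportion on room air among all randomised in each arm and e the fraction excluded, with no excluded patient on room air. The proportion in the four-infusion set is p / (1 − e). With p = 0.60:

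| Excluded, active / placebo | Active | Placebo | Spurious difference | Positive, four-infusion set |
|---|---|---|---|---|
| 15% / 15% | 0.60/0.85 = 70.6% | 70.6% | 0.0 points | 5% |
| 20% / 10% | 0.60/0.80 = 75.0% | 0.60/0.90 = 66.7% | +8.3 | 21% |
| 20% / 7.5% | 75.0% | 0.60/0.925 = 64.9% | +10.1 | 27% |
| 25% / 0% | 0.60/0.75 = 80.0% | 60.0% | +20.0 | 63% |
| 10% / 20% | 66.7% | 75.0% | −8.3 | 1% |

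The last column is from simulation (4,000 runs, Beta(1,1) priors). With all randomised patients it stays at 5 to 6%. For p between 0.50 and 0.70, the 20%/10% case ranges from +6.9 points (0.625 − 0.556) to +9.7 points (0.875 − 0.778).

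**Continuous outcome, no true effect**

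The sickest fraction e on a latent score is excluded, and the score correlates ρ with the standardised outcome. The mean shift in an arm is ρ × φ(z) / (1 − e), where z is the upper-e normal quantile and φ the normal density. The bias is the difference between arms. For 19%/9%, the factors φ(z) / (1 − e) are 0.335 and 0.178, difference 0.157. This gives 0.5 × 0.157 = 0.078 SD and 0.7 × 0.157 = 0.110 SD. Simulation (20,000 runs per scenario, flat prior, linear model) gives the following for ρ from 0.5 to 0.7:

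| Excluded, active / placebo | No covariate: bias (SD), positive | Covariate correlated 0.7–0.9 with score |
|---|---|---|
| 15% / 15% | 0.00, 5% | not run |
| 17% / 12% (15 of 100) | 0.04–0.05, 7–9% | 0.01–0.04, 6–8% |
| 19% / 9% (15 of 100) | 0.08–0.11, 10–13% | 0.02–0.07, 6–10% |
| 20% / 5% (14 of 100) | 0.12–0.17, 14–21% | 0.03–0.10, 7–14% |

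With all randomised patients, the bias stays within 0.003 SD and the positive rate is 4.8 to 5.2%. The reverse split, 9%/19%, gives −0.08 to −0.11 SD and 1 to 3% (8,000 runs, no covariate).

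**Conditional case: early recoverers miss infusions, true effect 0.5 SD, no covariate (6,000 runs)**

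At 17%/12% the estimate is 0.44 to 0.46 SD with about 70% positive. At 19%/9% it is 0.39 to 0.42 SD with 61 to 64% positive. All randomised gives about 79%, and random exclusion at the same rates about 73%. Only the gap below 73% is bias; the rest is lost sample size.

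**The case against.** - **The size rests on assumptions.** Arm-specific exclusion, a latent score that fully determines exclusion, and the 95% threshold are all assumed, and the simulated model is simpler than the SAP's treatment-by-time mixed model. With the covariates the SAP plans, the 19%/9% bias of 0.02 to 0.07 SD is about 0.1 to 0.3 of a standard error, taking √(1/51 + 1/34) = 0.22 SD. This stands. A looser link between score and exclusion gives less bias, and blinding limits discretionary differences between arms. But deterioration after baseline is not a baseline covariate, and blinding does not stop adverse events or deaths caused by treatment from differing by arm.
- **Excluded patients are still seen.** Safety-set tables cover every dosed patient, but SAP section 8 is descriptive. SAP 7.2.4.2 does model adverse events by arm. By 7.2.3 those models use the efficacy set, while 5.7 puts all safety evaluations in the safety set. The conflict is real, and it does not help the primary endpoints.
- **Stopping triggers may remove nobody.** That is correct if a part-given infusion counts as received. Withheld doses, discontinuation, withdrawal and death before the fourth infusion remove patients either way.
- **Early discharge is speculative.** Nothing says that discharge ends infusions, and some protocol text suggests outpatient visits. The last calculation is therefore conditional only, and the concern does not depend on it.
- **Deaths after the fourth infusion remain in the ordinal-scale analysis to Day 28.** True; the gap concerns earlier deaths.

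**Conclusion.** The concern holds and should be corrected before analysis. As written, both documents select efficacy patients on events after randomisation, and no all-randomised analysis is planned that could reveal the effect.

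Neither direction nor size can be known from the documents. With exclusions near the stated 15% and moderately uneven (19%/9%), the illustration gives about 0.1 SD without adjustment and 0.02 to 0.07 SD with a strong baseline covariate. False positives rise from 5% to 10–13% and 6–10% respectively. Equal exclusion of patients with equal prognosis gives no bias. Because the result depends on an assumption the trial cannot check within the set, the primary population should not rest on it.

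**What to change.** - Define the primary efficacy set as all randomised participants, analysed as randomised. A fallback is all randomised who received at least one blinded infusion.
- Use the data collected after infusions stop, where consent continues.
- State how death enters each endpoint. One workable choice: category 1 on the ordinal scale; room air and negative PCR counted as not reached; for markers and oxygenation, all values up to death in the mixed model, plus a sensitivity analysis ranking death as worst.
- Keep the four-infusion set as a labelled per-protocol sensitivity analysis, and say whether a part-given infusion counts. Keep the survivor analysis only as labelled supplementary.
- Reconcile SAP section 4 with 5.7, 7.1.4.1, 7.2.1, 7.2.3 and 7.2.4, including the set used for the adverse-event models.

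The cost is wording in the SAP, which is marked version 1.0, draft, and in the protocol. The SAP is dated November 2022 and reports in the past tense that no interim analyses were done, so conduct may be well advanced. The change should carry a dated reason and a statement of blinding status. Incomplete treatment may slightly dilute the estimated effect. Some marker data after stopping will be missing, because follow-up depends on consent, Day 28 has no marker sample, and that contact may be by telephone.
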